6.2.5 Prostate bed planning for IMRT

Planning Parameters

The plan will be deemed acceptable under the following conditions.

PTV: The dose marker levels for bladder and rectum have been modeled after prior studies in men treated definitively with IMRT for prostate cancer. At least 95% of the PTV should receive the prescribed dose (66 Gy); a variation will be noted if < 95% to 90% of the PTV receives the prescribed dose, and a protocol violation will be noted if < 90% of the PTV receives the prescribed dose. The maximum dose heterogeneity allowable in the PTV will be 10%; a variation will be > 10% and a violation > 15%. Since the dose is prescribed to the minimum isodose line of the PTV, the dose variability is seen in portions of the target volume receiving higher than the specified dose.

Rectum: Less than or equal to 25% and 45% of the rectum should receive ≥ 65 Gy and ≥ 40 Gy, respectively. A variation will be noted if up to an additional 7.5% of the rectal volume receives above the target doses specified. The inclusion of rectal volumes beyond these constraints will be considered a protocol violation.

Bladder: Less than or equal to 40% and 60% of the bladder (minus prostate bed CTV) should receive ≥ 65 Gy and ≥ 40 Gy, respectively. The criteria for the bladder have been relaxed because the dosimetric relationship of volume exposed to the specified marker doses is much less clear and the bladder neck is included in the CTV. A primary variation will be noted if up to an additional 7.5% of the bladder

volume receives above the target doses specified. The inclusion of bladder volumes beyond these constraints will be considered a secondary protocol variation; it will not be considered a protocol violation.

Femoral Heads: Less than or equal to 10% of each femoral head should receive ≥ 50 Gy. A variation will be noted if up to an additional 5.0% of either femoral head receives > 50 Gy.

Penile Bulb: The penile bulb may be outlined as a reference structure. No constraints will be placed on the penile bulb.

6.2.6 *Critical structures*

The critical normal structures are the bladder, rectum, and femoral heads. The normal tissues will be contoured and considered as solid organs.

- The bladder should be contoured from its base to the dome, excluding the CTV1 (the CTV1 includes the bladder neck).
- The rectum should be contoured from the anus (at the level of the ischial tuberosities) to the rectosigmoid flexure (this is roughly at about 10 cm) or for a maximum length of 15 cm if the sigmoid flexure is felt to be higher.
- Each femoral head should be outlined down to the interface between the greater and lesser trochanters.

6.2.7 *SRT documentation requirements*

The institution will archive treatment prescription and verification images for later review by the study chair if requested. For conformal RT, at least one port film or pretreatment alignment film per field along with the digital reconstructed radiographs (DRRs) from the treatment planning program or, alternatively, a simulation verification radiograph shall be acquired and kept for evaluation if requested except where geometrically impractical. For IMRT, at least one port film from each orthogonal film along with the digital reconstructed radiographs (DRRs) from the treatment planning program shall be acquired and kept for evaluation.

Note: Images are required to be taken but not submitted.

6.2.8 *Potential SRT adverse events*

All patients will be seen weekly by their radiation oncologist during radiation therapy. Any observations regarding radiation reactions will be recorded and should include attention toward the following potential side effects:

- Small bowel or rectal irritation manifesting as abdominal cramping, diarrhea, rectal urgency, proctitis, or hematochezia;
- Bladder complications including urinary frequency/urgency, dysuria, hematuria, urinary tract infection, and incontinence;
- Radiation dermatitis.

Clinical discretion may be exercised to treat side effects from radiation therapy. Examples of typical medications used in the management of rectal side effects, such as diarrhea, include diphenoxylate or loperamide. Bladder or rectal spasms are usually treated with anticholinergic agents or tolterodine. Bladder irritation

may be managed with phenazopyridine. Erectile dysfunction is often treated with medical management or mechanical devices. SRT adverse event reporting.

6.2.9 *Laboratory tests during SRT*

Standard of care practice during IMRT will be performed and includes the following assessments:

- Medical history, adverse event assessment, and medication review
- CBC with differential, Serum chemistries (see above)
- Physical examination and performance status with vital signs

Research visits during treatment will occur at day 1, 61, 92, 120, 151 and 180 +/-14 days according to the above schedule of events. Subjects will be referred back to registering institution if during the 6 weeks an AE is suspected.

6.3 *Removing Patients from the Protocol*

In the absence of treatment delays because of adverse events, treatment will continue for 6 months or until one of the following criteria applies:

- Patient decides to withdraw from the study
- Disease progression
- Symptomatic disease progression at any time
- Objective clinical disease progression
- Intercurrent illness that prevents further administration of treatment
- Unacceptable adverse event(s) that may or may not be directly related to treatment but that, in the judgment of the treating physician, makes it dangerous for the patient to be retreated
- General or specific changes in the patient's condition that render the patient unacceptable for further treatment, in the judgment of the investigator

Because an excessive rate of withdrawals can render the study uninterpretable, unnecessary withdrawal of patients should be avoided. When a patient discontinues treatment early, the investigator should make every effort to contact the patient and to perform a final evaluation. The reason(s) for withdrawal should be recorded.

6.4 *Concomitant Medications and Supportive Care*

Because of the potential for drug-drug interaction, the concurrent use of all other drugs, over-the-counter medications, and alternative therapies must be documented on the CRF. The principal investigator should be alerted if the patient is taking any agent found in Appendix B (a listing of medications with the potential for drug-drug interactions). Refer to Section 5.7 for concomitant medication guidelines.

7. *ADVERSE EVENTS*

7.1 *Definitions*

7.1.1 *Adverse Event (AE)*

An adverse event is any untoward medical occurrence in a research patient during a clinical study or within 30 days post-treatment, regardless of causality. This includes adverse clinical or laboratory findings, any adverse drug reaction (ADR), an illness with onset during the study, or an exacerbation of preexisting illness or condition.

7.1.2 *Serious Adverse Event (SAE)*

The investigator must assess each event to determine if it meets the criteria for classification as an SAE or serious adverse drug reaction.

All SAEs that occur any time a patient is on study (ie, as soon as the informed consent has been signed) or within 30 days of the last dose of enzalutamide must be recorded, regardless of the suspected relationship to enzalutamide. Any SAE occurring more than 30 days after the last dose of enzalutamide must be recorded if a causal relationship to enzalutamide is suspected.

An SAE/ADR as defined in the Code of Federal Regulations (21CFR312.32) is any event that:

- results in death
- is life-threatening
- results in inpatient hospitalization or prolongation of existing hospitalization
- results in persistent or significant disability or incapacity
- results in congenital anomaly or birth defect
- is medically significant in the opinion of the investigator

7.1.3 *Progression of malignancy*

Progression of a patient's malignancy should not be considered an AE, unless in the investigator's opinion, study treatment resulted in an exacerbation of the patient's condition. If disease progression results in death or hospitalization while on study or within 30 days of the last dose of enzalutamide, progressive disease will be considered an SAE.

7.1.4 *Life-threatening events*

A life-threatening event is any AE that places the patient at immediate risk of death from the reaction as it occurs. It is not a reaction that, had it occurred in a more severe form, might have caused death.

7.1.5 *Hospitalization or prolongation of hospitalization*

Hospitalization encompasses any inpatient admission (even for less than 24 hours) resulting from a precipitating, treatment-emergent adverse event. For chronic or long-term patients, inpatient admission also includes transfer within the hospital to an acute or intensive care inpatient unit. Hospitalizations for administrative reasons or a nonworsening preexisting condition should not be considered AEs (eg, admission for workup of a persistent pretreatment laboratory abnormality, yearly physical exam, protocol-specified admission, elective surgery). Preplanned treatments or surgical procedures should be noted in the baseline documentation. Hospitalization because of an unplanned event will be deemed an SAE.

Prolongation of hospitalization is any extension of an inpatient hospitalization beyond the stay anticipated or required for the original reason for admission.

7.1.6 *Significant disability*

Disability is a substantial disruption of the patient's ability to conduct normal life functions.

7.1.7 *Congenital anomaly*

If the female partner of a male patient becomes pregnant during the course of the study, the treating physician must be notified immediately. All confirmed pregnancies must be immediately reported to the SKCCC< Johns Hopkins and recorded in the consortium database. If the female partner becomes pregnant, we will seek permission to follow the pregnancy until resolution and assess for any effects related to the study drug. This will require the partner to sign a separate consent form.

7.1.8 *Medical significance*

An event that is not fatal or life-threatening and that does not necessitate hospitalization may be considered serious if, in the opinion of the investigator, it jeopardizes the patient's status and might lead to medical or surgical intervention to prevent any of the above outcomes. Such medically significant events could include allergic bronchospasm requiring intensive treatment in the emergency room or at home, blood dyscrasias that do not result in inpatient hospitalization, or the development of drug dependency or abuse.

The most recent version of the NCI CTCAE handbook will be used for adverse event descriptions and grading.

Follow-up of adverse events should continue until the event and any sequela resolve or stabilize at a level acceptable to the investigator and the study site/sponsor or medical monitor.

Events that are **not** considered serious adverse events include:

- routine treatment or monitoring of the studied indication, not associated with any deterioration in condition, or for elective procedures
- elective or pre-planned treatment for a pre-existing condition that did not worsen
- emergency outpatient treatment for an event not fulfilling the serious criteria outlined above and not resulting in inpatient admission
- respite care

7.2 *Expectedness*

Adverse events can be considered, "expected," or, "unexpected."

7.2.1 *Expected Adverse Events*

Expected adverse events are those that have been previously identified as resulting from administration of the agent. An adverse event can be considered expected

when it appears in the current adverse event list, the Investigator's Brochure, the package insert or is included in the informed consent document as a potential risk.

7.2.2 *Unexpected Adverse Events*

An adverse event can be considered unexpected when it varies in nature, intensity or frequency from information provided in the current adverse event list, the Investigator's Brochure, the package insert or when it is not included in the informed consent document as a potential risk. Contact the lead site, principal Investigator or sponsor to confirm unexpected adverse events when necessary.

7.3 Recording and Grading

7.3.1 *Recording*

All observed or volunteered adverse events, regardless of treatment group, severity, suspected causal relationship, expectedness, or seriousness will be documented.

A clinically significant change in a physical examination finding or an abnormal test result (ie, laboratory, x-ray, EKG) should be recorded as an AE, if it:

- is associated with accompanying symptoms
- requires additional diagnostic testing or medical or surgical intervention
- leads to a change in study dosing or discontinuation from the study
- requires additional concomitant drug treatment or other therapy, or
- is considered clinically significant by the investigator or ASMA

An abnormal test result that is subsequently determined to be in error does not require recording as an adverse event, even if it originally met one or more of the above criteria.

7.3.2 *Grading severity*

All adverse events will be graded for intensity on a scale of 0 to 5. Severity grades will be recorded and based on the most recent version of the NCI CTCAE handbook.

7.3.3 *Attributing causality*

After grading for severity, the investigator must evaluate all clinical AEs and abnormal laboratory values for possible causal relationship to enzalutamide. Causality attribution will be decided using the criteria outlined in Table 6.

Table 3 Relationship of Adverse Event to Study Drug

Relationship	Description
Unrelated	AE is clearly not related to enzalutamide
Unlikely	AE is doubtfully related to enzalutamide
Possible	AE may be related to enzalutamide
Probable	AE is likely related to enzalutamide
Definite	AE is clearly related to enzalutamide

Abnormal laboratory values of clinical significance that were present at baseline and did not change in severity or frequency during experimental therapy or intervention and those that can obviously be attributed to underlying disease will be recorded as unrelated and will not be considered when evaluating the AEs.

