5.2 Treatment Period

The following procedures are to be conducted each study visit on visit on Day 1, 61, 91, 120, 151 and 180 days while on study. Day 1, 61, 120 procedures should be done within seven days prior; day 91, 151 and 180 procedures should be done +/- 14 days (see Table 1):

- Review concurrent medications (see Appendix B for a listing of medications with the potential for drug interactions)
- Physical exam (vital signs, weight)
- ECOG performance status (Appendix A)
- Adverse events evaluation
- Review pill diary
- Laboratory tests (CBC w/diff, PSA, testosterone, comprehensive chemistry panel, including bilirubin, creatinine, SGOT[AST], SGPT[ALT])
- QoL questionnaires

The following procedures are to be conducted at each follow-up visit every 3 months ± 1 month up to 24 months (see Table 1). If participants are unable to return for follow-up, outside records may be obtained and assessments may be conducted via phone, email, or mail when possible:

- Review concurrent medications (see Appendix B for a listing of medications with the potential for drug interactions)
- Physical exam (vital signs, weight)
- ECOG performance status (Appendix A)
- Adverse events evaluation
- Laboratory tests (CBC w/diff, PSA, testosterone, comprehensive chemistry panel, including bilirubin, creatinine, SGOT[AST], SGPT[ALT])
- QoL questionnaires

The following procedure is to be conducted at each follow-up visit every 3 months ± 1 month past the first 24 months and up to 42 months (see Table 1):

- Laboratory test (PSA)

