5.2.2 Clinical and laboratory assessments

On day 1, 61, 91, 120, 151 and 180 visits while on study (Day 1, 61, 120 procedures should be done within seven days prior, day 91, 151, 180 procedures should be done +/- 14 days, see Table 1) patients will have non-fasting blood drawn for the following values:

- CBC w/diff
- Comprehensive chemistry panel
- PSA
- Testosterone

5.2.3 *Safety assessments*

Adverse events (AEs) will be monitored at each scheduled visit and throughout the study. Toxicity will be assessed using the most recent National Cancer Institute (NCI) guidance: the most recent version of Common Terminology Criteria for Adverse Events (CTCAE).

All nonserious AEs and SAEs, regardless of relationship to study treatment, will be collected from registration through the post-treatment visit and will be recorded in the subject's medical record and on the CRF. Following the post-treatment visit, only new treatment-related AEs and SAEs will be recorded. Seizures (regardless of causality) will be recorded throughout the study.

5.2.3.1 *Seizures*

Seizures that occur at any time during the study, regardless of causality, severity, or outcome, will be recorded in the subject's medical record and on the CRF.

5.3 **Treatment-Limiting Adverse Event**

A treatment-limiting adverse event is any AE related to protocol therapy experienced during the study resulting in treatment termination.

5.4 **Dose Modifications**

Patients enrolled in this study will be evaluated clinically and with standard laboratory tests before and at regular intervals during their participation in this study as specified in Section 6. The most recent NCI CTCAE will be used to grade adverse events.

At each study visit for the duration of their participation in the study, patients will be evaluated for adverse events (all grades), serious adverse events (SAEs), and adverse events that require study drug interruption or discontinuation. Patients discontinued from the treatment phase of the study for any reason will be evaluated approximately 30 days after the last dose of the study drug.

If patients either require that the study drug be discontinued because of an adverse event (as described below) or have a treatment interruption of greater than 2 weeks for enzalutamide or placebo, at the investigator's discretion, they may continue on SRT until completion of the SRT.

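### Causality is rated against enzalutamide only and the late recording rules conflict, so late radiation toxicity can be recorded incompletely or unevenly across sites

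*Combined protocol and SAP*

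**What the plan says.** **Attribution.** Section 7.3.3 states that "the investigator must evaluate all clinical AEs and abnormal laboratory values for possible causal relationship to enzalutamide". All five rows of Table 3 are worded the same way; the strongest category reads "AE is clearly related to enzalutamide". There is no scale for SRT, although SRT is part of both arms (sections 5 and 5.2.1). Section 6.2.8 lists the reactions expected from it, for example "Small bowel or rectal irritation manifesting as abdominal cramping, diarrhea, rectal urgency, proctitis, or hematochezia", along with urinary effects and dermatitis.

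**Recording.** Section 5.2.3 begins without a filter: "All nonserious AEs and SAEs, regardless of relationship to study treatment, will be collected from registration through the post-treatment visit". It then narrows: "Following the post-treatment visit, only new treatment-related AEs and SAEs will be recorded". On late SAEs, section 7.1.2 says: "Any SAE occurring more than 30 days after the last dose of enzalutamide must be recorded if a causal relationship to enzalutamide is suspected". Section 7.3.1 sets neither a causal condition nor a time limit: "All observed or volunteered adverse events, regardless of treatment group, severity, suspected causal relationship, expectedness, or seriousness will be documented".

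**Follow-up and analysis.** Section 5.2 says: "The following procedures are to be conducted at each follow-up visit every 3 months ± 1 month up to 24 months", and adverse event evaluation is on that list. Section 10.1.2 plans to describe safety in Arm A and Arm B, including the relationship of events to study therapy.

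**The concern.** Whether enzalutamide adds to radiation toxicity is a natural safety question for this combination. Section 1.3.1 itself reports that an earlier antiandrogen trial found no significant addition to radiation toxicity. That trial used another drug and 64.8 Gy, against 66.6-70.2 Gy here, so this trial needs its own late data.

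Rating one event at a time cannot answer the question. If enzalutamide made ordinary radiation proctitis or cystitis more frequent, each case would still look like a radiation effect, and an investigator could reasonably rate it unlikely to be due to the drug. The excess would show only in a comparison of all such events by arm. A recording rule that depends on attribution, with an enzalutamide scale as the only tool, can remove the events that this comparison needs.

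**Working it through.** No figure in the plan is at issue. The check compares the recording rules and then does date arithmetic on the plan's own schedule.

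**Step 1: the rules side by side**

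| Section | Events | Period | Condition on cause |
|---|---|---|---|
| 5.2.3, first rule | AEs and SAEs | registration to post-treatment visit | none |
| 5.2.3, second rule | AEs and SAEs | after that visit | new and treatment-related (undefined) |
| 7.1.2, first rule | SAEs | from consent while on study, or within 30 days of last dose | none |
| 7.1.2, second rule | SAEs | more than 30 days after last dose | enzalutamide suspected |
| 7.3.1 | all AEs | not stated | none |
| 7.4.2 | AEs and SAEs | consent to at least 30 days after SRT | none |
| 6.2.8 | radiation reactions | set alongside weekly visits during SRT | none |

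**Step 2: apply them to a late event**

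- *New, non-serious proctitis in follow-up, judged due to SRT.* If treatment-related in 5.2.3 means related to any assigned treatment, it is recorded. If the site uses the only scale supplied (Table 3), it rates as unlikely or unrelated and is not. Under 7.3.1 it is recorded.
- *A serious event in a man still on study.* The first rule of 7.1.2 requires recording whatever the cause. The second rule creates a duty only if enzalutamide is suspected. Section 5.2.3 depends again on the undefined term.
- *An earlier event that worsens.* It is not new under 5.2.3, but 7.1.8 and 7.4.2 require adverse events to be followed until they resolve or stabilize.

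Two sites can therefore follow the protocol and record differently.

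**Step 3: when the filter starts**

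Inputs: SRT starts between day 61 and day 92 and lasts 7-8 weeks, or 49-56 days (synopsis). Study drug ends on day 180 (Table 1). The evaluation after discontinuation is about 30 days after the last dose (5.4). Section 5.5 allows 30 days either side of the last dose, so day 210 is the late edge.

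- SRT ends between day 61 + 49 = 110 and day 92 + 56 = 148 (Table 1: day 120).
- The post-treatment visit is at the latest about day 180 + 30 = 210.
- Gap from the end of SRT: 210 - 148 = 62 to 210 - 110 = 100 days (Table 1: 210 - 120 = 90).
- The minimum window in 7.4.2 ends between day 110 + 30 = 140 and day 148 + 30 = 178.

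The documents give no cut-off for late toxicity. If late means beyond about 90 days after SRT (an assumption), the late period opens between day 110 + 90 = 200 and day 148 + 90 = 238. Nearly all late toxicity then falls under the second rule of 5.2.3, and the 7.4.2 minimum does not reach it.

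**Step 4: how much assessment is affected**

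Follow-up visits: 24 / 3 = 8 per man. Scheduled evaluations: 8 x 96 = 768. This is a ceiling on evaluations exposed to the conflict, not a count of lost events. Men who leave at PSA progression and the plan's 15% allowance for loss to follow-up both reduce it.

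**Step 5: effect on the comparison**

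Let pA and pB be the true late event rates and c the share recorded, equal in both arms. The recorded difference is c(pB - pA), which shrinks as c falls. The assessor is blinded and center is a stratification factor (4.1.3), so c need not differ by arm. The expected harm is fewer events and unreliable absolute rates, rather than a bias of known direction.

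**The case against.** A reader might infer that late radiation toxicity is simply lost in both arms. The documents do not support that.

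- **Treatment-related need not mean enzalutamide-related.** Section 5.2.3 does not cite Table 3. SRT is assigned treatment in both arms, Table 2 lists it in the study drug column, and sections 5.3, 7.4.1 and 10.1.2 use wider terms (protocol therapy, study drug/treatment, study therapy).
- **Serious events have a rule without a causal condition.** One might infer that a late hospitalization for a radiation effect goes unrecorded. But 7.1.2 also requires every SAE while a patient is on study, and footnote 8 of Table 1 keeps men on study until PSA progression. The enzalutamide sentence says when recording is mandatory; it does not order other events to be discarded.
- **General rules point to full capture.** Section 7.3.1 documents all events, and 7.4.2 puts all AEs and SAEs on source documents and, for eligible subjects, in the CRFs. Ongoing events are followed until stable, so a worsening rectal event is not plainly lost.
- **Quality-of-life questionnaires** continue at the follow-up visits.

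All of this stands against a claim of certain loss. It does not remove the conflict. Section 7.3.1 states no period, while 5.2.3 is specific to the late period and says only. The full-capture text in 7.4.2 sits in a section whose stated minimum ends 30 days after SRT. No text gives an investigator a category for an SRT-related event. Questionnaires are not adverse event records.

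**Conclusion.** The point holds as an internal conflict in the recording rules, combined with an attribution scale that omits one of the two treatments. Followed as written, the plan can yield late bladder and bowel data that are incomplete and site-dependent, which weakens the by-arm safety comparison. The exposure is clearest for new, non-serious events after the post-treatment visit.

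The size of the loss cannot be derived from the documents. They give no late toxicity rate and do not show how sites read 5.2.3. For new, non-serious radiation events the loss lies anywhere between none (every site takes the wide reading) and all (every site applies Table 3). Any number of men per arm would require an assumed event rate and assumed total loss.

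The timing result rests on a post-treatment visit near day 210 and on an assumed threshold of about 90 days for late effects. Safety is a secondary objective, and FFPP and its analysis are unaffected. This should be fixed, but it does not threaten the primary result.

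**What to change.** 1. Reconcile 5.2.3, 7.1.2, 7.3.1, 7.3.3 and 7.4.2 so that one rule states which events are recorded, for how long and under what condition. Define treatment-related.
2. In 7.3.3 and Table 3, rate each adverse event twice: against blinded study drug and against SRT. Correct the references to Table 6 in 7.3.3 and 7.4.1, since the table is numbered 3.
3. At the existing 3-monthly visits to 24 months, record new or worsened bladder and bowel events of the types listed in 6.2.8 regardless of attribution. Section 5.2.3 already handles seizures this way throughout the study.
4. Tabulate these events by arm in the safety population of 10.2.2. Section 10.3.1 now limits adverse event summaries to patients who received enzalutamide and needs to cover both arms.

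The cost is protocol wording, one extra attribution field and more adverse event entries. No new visit or procedure is needed. Late events already left unrecorded may be hard to recover, so any site that used the narrow reading should be identified when the safety data are reported.

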Finally, provocative preliminary Phase II data presented at the ASCO 2013 by Mathew Smith and colleagues assessed the efficacy and safety of 25-weeks (~6-mos) of enzalutamide alone in prostate cancer of all stages who had never received hormone therapy; presenting with non-castrate testosterone levels (≥ 230 ng/dL). Enzalutamide alone for 6-mos achieved a high PSA response rate with efficacy similar to castration, but in contrast to castration, BMD remained stable and metabolic variables were not substantially impacted.

The trial described here differs from RTOG 96-01, GETUG-16, RTOG 05-34 and RADICALS in several ways. First, the eligibility criteria are stricter; less favorable patients have been selected and relative to RTOG 96-01 contemporary patients with modern radiotherapy dose and techniques are being used. Second, short-term ARB is being tested, while in RTOG 96-01 and RADICALS long-term ARB of 2-years was examined. Finally, and most importantly, we are testing the second generation ARB agent, enzalutamide, alone in combination with SRT as opposed to GETUG-16, RTOG 05-34 and RADICALS which use AD.

This trial is not intended to address the efficacy of SRT alone over observation. The complete response rate (a drop in PSA to undetectable levels) after SRT is 70%-80% and durable responses are observed in 30%-40% of patients. For these reasons, it is not feasible or appropriate to randomize men between observation and SRT. The more important issue is whether the proportion of durable responses is increased by altering the therapeutic approach, such as the use of enhanced ARB using enzalutamide. Similarly, as described above, there is considerable controversy regarding the benefit of adding high-dose bicalutamide to men with rising PSA where there PSA is < 0.7 following surgery. Given differences in this old trial consisting of lower SRT dose of 64.8 Gy, and the non-contemporary study population we think it is reasonable to offer SRT alone as a control arm as long as men are informed of the survival results of RTOG 96-01 and the controversy regarding this study in the modern era.

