10.1.2 Analysis of secondary endpoints

The first secondary endpoint is time to local recurrence within the radiation field, defined as the time from randomization to the date of local recurrence of disease. Subjects who do not have local recurrence will be censored on the date of their last evaluable tumor assessment for local recurrence. Subjects who start any subsequent anti-cancer therapy without a prior reported local recurrence will be censored at the last evaluable tumor assessment prior to initiation of the subsequent anti-cancer therapy.

The second secondary endpoint is metastasis free survival (MFS), defined as the time from randomization to the date of metastasis or death from any cause up to 90 days following the last response assessment, whichever occurs first. A subject who does not have metastasis and is alive will be censored at the last date of tumor assessment.

Time-to-event endpoints (time to local recurrence and MFS) will be analyzed similarly as described for the primary endpoint (FFPP).

Safety and tolerability will also be evaluated as secondary objectives. For safety analysis, overall safety profile and toleration of Arm A and Arm B will be characterized by type, frequency, severity, timing and relationship of study therapy of adverse events and laboratory abnormalities. Adverse events will be summarized by the frequency of patients experiencing treatment emergent adverse events corresponding to body systems and by worst NCI CTCAE (version 4.0) grade.

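### Section 7.3.3 can be read as letting a causality call remove new or worsened on-treatment laboratory abnormalities from the AE evaluation, which does not fit the all-causality summaries in section 10

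*Combined protocol and SAP*

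**What the plan says.** Section 7.3.3 opens by giving the attribution task to the investigator: "the investigator must evaluate all clinical AEs and abnormal laboratory values for possible causal relationship to enzalutamide". Its last sentence then deals with clinically significant abnormal laboratory values of two kinds. The first kind is those "that were present at baseline and did not change in severity or frequency during experimental therapy or intervention". The second kind is "those that can obviously be attributed to underlying disease will be recorded as unrelated and will not be considered when evaluating the AEs". The treatment in that sentence applies to both kinds.

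Other sections bear on the same data:

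- **7.3.1** sets the recording rule: "All observed or volunteered adverse events, regardless of treatment group, severity, suspected causal relationship, expectedness, or seriousness will be documented". It lists conditions that each make an abnormal test result an AE. One is that the result "is considered clinically significant by the investigator or ASMA". There is no exception for underlying disease.
- **7.1.1** defines an AE without regard to cause. It includes adverse laboratory findings and the worsening of a condition the patient already had.
- **5.2.3** collects AEs up to the post-treatment visit whatever their suspected cause.
- **10.1.2**, repeated in **10.4.3**, characterizes both arms by type, frequency, "severity, timing and relationship of study therapy of adverse events and laboratory abnormalities".
- **10.3.1** arranges the AE summaries by, among other things, causality.
- **10.3.3** provides a separate summary of a chosen set of laboratory parameters.

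**The concern.** The first limb of the 7.3.3 sentence is tied to baseline and removes only background. The second is tied to nothing but a judgement about cause. A laboratory value that appears or worsens after study drug starts can meet it, and the sentence then gives two separate instructions: code the value as unrelated, and leave it out when the AEs are evaluated.

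A placebo-controlled trial can compare all-cause rates between arms without relying on individual causality calls. If events are screened by those calls first, a drug effect that an investigator puts down to disease is lost from the count together with the background. Safety is a secondary objective, so the AE tables should have one unambiguous content. As written, two analysts could build different tables from the same data: one dropping these values under 7.3.3, the other keeping them under section 10.

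**Working it through.** The documents give no figure on this point, so there is nothing to recompute. The check sets the passages side by side.

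1. **Does the second limb reach on-treatment values?** Yes. The baseline condition belongs to the first limb only. The second limb starts afresh and carries no condition on timing or change.

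2. **Is the exclusion distinct from the causality code?** Yes, on the wording. The sentence first assigns the code and then adds that the values are not considered. If only the code were meant, the second instruction would be redundant.

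3. **What does evaluating the AEs refer to?** It is not defined. It could mean the causality step, since 7.3.3 uses the same verb in its opening line. It could also mean the safety analysis, since section 10.3.1 is headed as the evaluation of adverse events. The second reading is at least as natural.

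4. **Do the analysis sections allow for an exclusion?** No. In 10.1.2 and 10.4.3, relationship stands in a list with type, frequency, severity and timing, as one descriptor of both AEs and laboratory abnormalities. In 10.3.1, causality is one way of arranging the tables. None of the three refers to 7.3.3 or states that events attributed to disease are left out. Section 7.3.3 applied in full and these summaries delivered in full cannot both be had.

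5. **Does the AE definition allow for it?** No. Under 7.1.1, a worsening of an existing condition is an AE. A laboratory value showing such a worsening could be counted under 7.1.1 and set aside under 7.3.3.

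6. **Is the second limb needed to keep cancer progression out of the AE tables?** No. Section 7.1.3 already says when progression is and is not an AE. Entry under 3.3 requires non-metastatic disease and a PSA below 0.7 ng/mL, so there should be little laboratory abnormality, apart from PSA, that plainly comes from the cancer.

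7. **Does 7.3.1 conflict with 7.3.3?** No. Section 7.3.1 requires that events be documented. Section 7.3.3 still has the values recorded, with a causality code. Both can be met. The mismatch arises later, at evaluation.

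8. **Does anything recover the excluded values?** In part. The results stay in the database, and 10.3.3 summarizes laboratory parameters with no causality condition. It covers a selection, however, and the selection is not specified.

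**The case against.** The strongest reply is that the sentence sits under a causality heading and means only that such values are coded unrelated and need no further causality grading. No analysis section adopts an exclusion, section 5.2.3 collects events whatever their cause, and 10.3.3 reports laboratory changes anyway. This reading is possible, but it leaves the second instruction in the sentence with no work to do. The ambiguity is itself a reason to settle the wording.

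Several limits on the concern stand in full. The rule covers laboratory values only, not clinical AEs. The attribution must be obvious, although no criterion is given. Underlying disease is undefined, and the protocol elsewhere uses a different term for comorbid conditions, so extending it to any comorbidity is an inference.

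Three stronger readings are tempting and are not supported:

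- **That 7.3.3 contradicts 7.3.1.** It does not, because documentation and later exclusion are different steps.
- **That the comparison is biased between arms.** Section 4.1.3 blinds the investigator, and the documents give no basis for a direction or size of differential attribution. Blinding does not prevent under-counting in both arms.
- **That the rule would protect a claim of metabolic safety.** The statement in 1.3.3 that "metabolic variables were not substantially impacted" is background from another study. Section 2.2 sets no metabolic objective, blood is drawn non-fasting (5.2.2), and the chemistries listed under Table 1 include no lipids.

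**Conclusion.** The point holds as an internal inconsistency of minor severity. Followed as written, 7.3.3 can under-count treatment-emergent laboratory AEs on the strength of a blinded causality judgement. That is inconsistent with the all-causality summaries in 10.1.2, 10.3.1 and 10.4.3 and with the AE definition in 7.1.1.

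The size cannot be derived: the documents give neither an expected rate of laboratory abnormalities nor the share likely to be attributed to disease. Any percentage-point effect would be invented. The conclusion rests on reading the exclusion as separate from the causality code. If only attribution was intended, the remaining defect is unclear wording. The primary endpoint, sample size and error rates are unaffected.

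**What to change.** In 7.3.3, confine the exclusion to laboratory values present at baseline and unchanged. Add that attribution to underlying disease affects the causality field only. Any laboratory abnormality that is new or worse than at baseline and meets 7.3.1 then stays in the AE tables of both arms at its CTCAE grade, with the attribution shown. Section 7.1.3 on progression stays as it is.

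The cost is a short wording change and a few more rows marked unrelated in the AE tables. No new data, visits or analyses are needed.
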